NAME OF COMPANY BioMarin Pharmaceutical Inc. [name] NAME OF FINISHED PRODUCT: BMN 270 NAME OF ACTIVE INGREDIENT: AAV5-hFVIII-SQ	SUMMARY TABLE Referring to Part of the Dossier: Volume: Page: Reference:	FOR NATIONAL AUTHORITY USE ONLY:

Tertiary efficacy endpoints:
 
 • Change from baseline in the EQ-5D-5L score at Week 52 post-BMN 270 infusion. • Change from baseline in the Work Productivity and Activity Impairment plus Classroom Impairment Questions: Hemophilia Specific (WPAI+CIQ:HS) score at Week 52 post-BMN 270 infusion. • Change from baseline in Patient Reported Outcomes, Burdens, and Experiences (PROBE) score at Week 52 post-BMN 270 infusion. 
Safety:
 
The following safety outcome measurements will be assessed:
 
 • Incidence of adverse events (AEs) and serious AEs (SAEs) • Change in clinical laboratory tests (serum chemistry and hematology) • Change in vital signs • Change in physical examination • Vector shedding (blood, urine, semen, stool, saliva) • Liver tests (LTs, including ALT, AST, GGT, lactate dehydrogenase [LDH], total bilirubin, and alkaline phosphatase) 
 ◦ The frequency and duration of LT testing may be changed based on discussion between the Medical Monitor and the Investigator, review of subject data, and/or by independent DMC feedback. • Immune response to FVIII transgene product and AAV5 capsid proteins • Immunological assessments, including hFVIII TAb, interferon gamma (IFNg) ELISpot, complement, and an exploratory biomarker panel. 
There will be a detailed assessment of cellular and humoral responses to AAV5 capsid and FVIII protein.
 
Pharmacodynamics:
 
The FVIII protein concentration and activity level as measured by a validated immunoassay and a validated FVIII activity assay, respectively, will be used for plasma profiles; FVIII protein and activity will be used to determine PD parameters.
		

NAME OF COMPANY	SUMMARY TABLE	FOR NATIONAL AUTHORITY USE ONLY:
BioMarin Pharmaceutical Inc. [name]	Referring to Part of the Dossier:	
NAME OF FINISHED PRODUCT: BMN 270	Volume:	
NAME OF ACTIVE INGREDIENT: AAV5-hFVIII-SQ	Page:	
STATISTICAL METHODS:		
Sample Size		
Approximately 20 subjects may be dosed in the study, including at least 16 subjects who are AAV5 antibody-negative and up to 25% of the total number of subjects who have an AAV5 antibody titer that is detectable but below the minimum required dilution at Screening.		
For the primary endpoint, a sample size of 16 will provide 85% power to demonstrate that the change in hFVIII activity during Weeks 49-52 from baseline is greater than 0, assuming an effect size of 0.8, using a one-sample t-test at the 1-sided significance level of 0.025 (or equivalently, at the 2-sided significance level of 0.05). The effect size of 0.8 is assumed conservatively based on the results from 270-201 and the interim results from 270-301.		
Analysis Population		
The intention-to-treat (ITT) population is defined as all subjects who received BMN 270 infusion. The ITT population will be the primary population for safety analyses, as well as being used for supportive efficacy analyses.		
The modified intention-to-treat (mITT) population is the primary analysis population for efficacy for this study. The mITT population will include all subjects who received BMN 270 infusion and who were AAV5 antibody negative at Screening (ie, excludes subjects with an AAV5 antibody titer detectable but below the minimum required dilution).		
Subjects with an AAV5 antibody titer detectable but below the minimum required dilution will be used for exploratory efficacy analysis on FVIII activity, as measured by chromogenic substrate assay, during Weeks 49-52 post-BMN 270 infusion.		
Analysis		
For the primary efficacy endpoint at Week 52 (ie, the change in the hFVIII activity during Weeks 49-52 post-BMN 270 infusion from baseline, as measured by chromogenic substrate assay), a one-sample t-test will be used to test the null hypothesis that the change is 0 or less against the alternative hypothesis that the change is greater than 0. Baseline value of 1 IU/dL (eligible subjects must have residual FVIII levels \leq 1 IU/dL as evidenced by medical history) will be used in the calculation of change from baseline since all the subjects will be on prophylactic hemophilia therapy prior to BMN 270 infusion where the FVIII activity level cannot be reliably measured. Descriptive summaries of the proportions of subjects whose FVIII activity during Weeks 49-52 is greater than or equal to select thresholds, such as 5, 15, 25, 30, and 40 IU/dL, and the confidence intervals of the proportions will also be provided.		
The analyses of the secondary and tertiary efficacy endpoints will be descriptive. Mean and associated 95% confidence interval will be provided for the following secondary endpoints, where the baseline value will be derived from the data in the approximately 12-month period prior to BMN 270 infusion:		

NAME OF COMPANY	SUMMARY TABLE	FOR NATIONAL AUTHORITY USE ONLY:
BioMarin Pharmaceutical Inc. [name]	Referring to Part of the Dossier:	
NAME OF FINISHED PRODUCT: BMN 270	Volume:	
NAME OF ACTIVE INGREDIENT: AAV5-hFVIII-SQ	Page: Reference:	

 • Change from baseline in the annualized utilization (IU/kg/year) of exogenous FVIII replacement therapy during Weeks 5-52 post-BMN 270 infusion, for subjects receiving FVIII prophylaxis during the 12 months prior to study entry, or change from baseline in the annualized utilization (mg/kg/year) of emicizumab during Week 27 to Week 52 post-BMN 270 infusion for subjects receiving prior emicizumab prophylaxis • Change from baseline in the annualized infusion rate (number/year) of exogenous FVIII replacement therapy during Weeks 5-52 post-BMN 270 infusion, for subjects receiving FVIII prophylaxis during the 12 months prior to study entry, or change from baseline in the annualized utilization (mg/kg/year) of emicizumab during Week 27 to Week 52 post-BMN 270 infusion for subjects receiving prior emicizumab prophylaxis • Change from baseline in the annualized number of bleeding episodes (number/year) requiring exogenous FVIII replacement treatment during Weeks 5-52 post-BMN 270 infusion for subjects receiving prior FVIII prophylaxis, or Weeks 27-52 post-BMN 270 infusion for subjects receiving prior emicizumab prophylaxis from baseline 		

Mean change from baseline and associated 95% confidence interval will be calculated for the total score of Haemo-QoL-A at Week 52 post-BMN 270 infusion as well.
		

The incidence of AEs will be summarized by system organ class, preferred term, relationship to study drug, seriousness, and severity. Clinical laboratory test values, vital signs, vector shedding and immune response parameters will be summarized descriptively by visit.
		

The final analysis for the study will be performed after all subjects have been followed for 52 weeks post-BMN 270 infusion (or have discontinued study participation prior to Week 52). No formal interim analysis is planned. Informal analyses (ie, no hypothesis testing) may be performed at different timepoints to assess efficacy and safety over time. The primary efficacy endpoint for such analyses involves hFVIII activity, as measured by chromogenic substrate assay, and is defined as median FVIII activity during a specific 4-week time interval post-BMN 270 infusion.
		

Details of the planned analyses will be specified in the SAP.
		

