14.3 Secondary Efficacy Endpoints

The analyses of the secondary efficacy endpoints will be descriptive. Mean and associated 95% confidence interval will be provided for the following secondary endpoints, where the baseline value will be derived from the data in the approximately 12-month period prior to BMN 270 infusion:

- Change from baseline in the annualized utilization (IU/kg/year) of exogenous FVIII replacement therapy during Weeks 5-52 post-BMN 270 infusion, for subjects receiving FVIII prophylaxis during the 12 months prior to study entry, or change from baseline in the annualized utilization (mg/kg/year) of emicizumab during Week 27 to Week 52 post-BMN 270 infusion for subjects receiving prior emicizumab prophylaxis
- Change from baseline in the annualized infusion rate (number/year) of exogenous FVIII replacement therapy during Weeks 5-52 post-BMN 270 infusion, for subjects receiving FVIII prophylaxis during the 12 months prior to study entry, or change from baseline in the annualized utilization (mg/kg/year) of emicizumab during Week 27 to Week 52 post-BMN 270 infusion for subjects receiving prior emicizumab prophylaxis
- Change from baseline in the annualized number of bleeding episodes (number/year) requiring exogenous FVIII replacement treatment during Weeks 5-52 post-BMN 270 infusion for subjects receiving prior FVIII prophylaxis, or Weeks 27-52 post-BMN 270 infusion for subjects receiving prior emicizumab prophylaxis

Mean change from baseline and associated 95% confidence interval will be calculated for the total score of Haemo-QoL-A at Week 52 post-BMN 270 infusion as well.

The missing value of the change for annualized utilization and annualized infusion rate will be imputed as 0. The missing value of the change for annualized number of bleeding episodes will be imputed using the median value of the changes of all observed cases.

A sensitivity analysis is planned to analyze ABR using a generalized linear mixed model assuming negative binomial as the underlying distribution. The model will include period (pre- to post-BMN 270 infusion) as the only factor, repeated within subject. The actual number of bleeding episodes will be used as the dependent variable with the time period adjustment (annualization) being implemented as the offset.

To assess the impact of missing data, analyses using observed case are planned as sensitivity analyses for the secondary endpoints. Multiple imputation methods may also be performed.

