
 1. Any condition that, in the opinion of the Investigator or a hepatologist or radiologist, would make liver biopsy contraindicated. This includes (but is not limited to): abnormalities detected on liver ultrasound performed within 28 days of procedure or prior liver ultrasound result within 90 days that would preclude safe performance of the biopsy. 		

NAME OF COMPANY	SUMMARY TABLE	FOR NATIONAL AUTHORITY USE ONLY:
BioMarin Pharmaceutical Inc. [name]	Referring to Part of the Dossier: Volume:	
NAME OF FINISHED PRODUCT: BMN 270	Page:	
NAME OF ACTIVE INGREDIENT: AAV5-hFVIII-SQ	Reference:	
INVESTIGATIONAL PRODUCT(S), DOSE, ROUTE AND REGIMEN: Each subject will receive a single intravenous infusion of BMN 270 at 6E13 vg/kg. The volume of infusion will depend on the subject's weight		
REFERENCE THERAPY(IES), DOSE, ROUTE AND REGIMEN: No reference therapy will be evaluated in this study.		
DURATION OF TREATMENT: BMN 270 is given as a single dose by intravenous infusion.		
CRITERIA FOR EVALUATION: Efficacy: Primary efficacy endpoint: 
 Change of the hFVIII activity, as measured by chromogenic substrate assay, during Weeks 49-52 post-BMN 270 infusion from baseline. Each subject's hFVIII activity during Weeks 49-52 is defined as the median of the values obtained during this 4-week window. Values for hFVIII activity will be excluded if obtained within 72 hours since the last infusion of exogenous FVIII protein concentrates. Secondary efficacy endpoints: 
 Change from baseline in the annualized utilization (IU/kg/year) and infusion rate (number/year) of exogenous FVIII replacement therapy during Week 5 to Week 52 post-BMN 270 infusion, for subjects receiving FVIII prophylaxis during the 12 months prior to study entry or change from baseline in the annualized utilization (mg/kg/year) of emicizumab during Week 27 to Week 52 post-BMN 270 infusion for subjects receiving prior emicizumab prophylaxis. Change from baseline in the annualized number of bleeding episodes requiring exogenous FVIII replacement treatment (annualized bleeding rate, ABR) during Week 5 to Week 52 post-BMN 270 infusion for subjects receiving prior FVIII prophylaxis, or Week 27 to Week 52 post-BMN 270 infusion for subjects receiving prior emicizumab prophylaxis Change from baseline in the total score of Haemo-QoL-A at Week 52 post-BMN 270 infusion 		

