In subjects who experience recurring bleeding episodes, the Investigator and Medical Monitor will discuss whether to resume prior FVIII prophylaxis. Subjects who do not respond to BMN 270 treatment (ie, treatment failure, manifesting as either failure to achieve FVIII activity \geq 5 IU/dL by Week 52 or inability to maintain independence from prophylactic FVIII replacement therapy due to joint bleeding episodes, in the judgment of the Investigator) may, at the Investigator's discretion and after discussion with the Medical Monitor or Sponsor-designated Data Monitor, follow an abbreviated visit schedule after Week 52 of the study by attending only the Q12W and End of Year visits during Years 2-5. Subjects who are not attending the Q4W/Q6W visits during Years 2-5 may receive a scheduled monthly follow-up telephone call from the site to ask about adverse events, concomitant medications, and bleeding events/FVIII replacement usage.

There will be an ongoing review of individual subject safety by the Medical Monitor, and both safety and efficacy data by the DMC. Patients will receive prophylactic corticosteroids with tapering of the dosage based upon consideration of ALT values, FVIII activity levels, and consultation with the Investigator and the Medical Monitor. Therapeutic oral corticosteroids may be initiated if a subject's ALT values increase from baseline levels, after consultation between the Investigator and the Medical Monitor.

In case of a safety concern, additional unscheduled laboratory tests may be performed locally (at the Investigator's discretion) in order to facilitate timely and appropriate clinical management decisions; where possible, a matched sample for testing at the central laboratory should be collected (using the Unscheduled Visit lab kit) at the same time as the local unscheduled sample.

Any safety signal may trigger a review of the data and possible additional immunogenicity studies or other diagnostics deemed necessary that include an assessment of cellular immune responses using collected peripheral blood mononuclear cells (PBMCs).

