9.7.3 Secondary Efficacy Variables

9.7.3.1 Factor VIII Replacement Therapy/Bleeding Episodes

Secondary efficacy variables include:

- Change in the annualized utilization (IU/kg/year) and infusion (number/year) rates of exogenous FVIII replacement therapy during Week 5 to Week 52 post-BMN 270 infusion from the baseline number and utilization of exogenous FVIII replacement therapy, for subjects receiving FVIII prophylaxis during the 12 months prior to study entry, or change in administration of exogenous FVIII replacement therapy Week 27 to Week 52 post-BMN 270 infusion for subjects receiving prior emicizumab prophylaxis.
- Change in the annualized number of bleeding episodes requiring exogenous FVIII replacement treatment (annualized bleeding rate, ABR) during Week 5 to Week 52 post-BMN 270 infusion for subjects receiving prior FVIII prophylaxis, or Week 27 to Week 52 post-BMN 270 infusion for subjects receiving prior emicizumab prophylaxis, from the baseline ABR during the 12 months prior to study entry.

Subjects must have high quality documented historical data available concerning previous bleeding episodes and hemophilia treatment over the previous 12 months in order to be eligible to enroll in the study. During the study, subjects will be asked at each study visit to

report the use of factor replacement therapy and the number of bleeding episodes since the previous visit. This information will be captured on the subject's diary or other subject records.

Subjects are strongly encouraged to immediately consult Investigator for guidance regarding exogenous FVIII administration for suspected bleeds or bleeding episodes within the first 30 days post-BMN 270 infusion.

In subjects who experience recurrent bleeding episodes, the Investigator and Medical Monitor will discuss whether to resume prior FVIII prophylaxis or use of emicizumab.

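### For subjects who entered on FVIII prophylaxis, the therapy-use endpoint does not count emicizumab, so a treatment failure moved to emicizumab would score close to a full responder

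*Protocol*

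**What the plan says.** **Endpoint.** The Amendment 1 synopsis (Secondary efficacy endpoints) defines therapy use in prior-FVIII subjects as "Change from baseline in the annualized utilization (IU/kg/year) and infusion rate (number/year) of exogenous FVIII replacement therapy during Week 5 to Week 52". The Analysis part of the synopsis repeats this for the infusion rate: "Change from baseline in the annualized infusion rate (number/year) of exogenous FVIII replacement therapy during Weeks 5-52". Emicizumab is measured only in the other stratum: "emicizumab during Week 27 to Week 52 post-BMN 270 infusion for subjects receiving prior emicizumab prophylaxis".

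**Analysis.** "Mean and associated 95% confidence interval will be provided for the following secondary endpoints". The scale is absolute change (IU/kg/year and infusions/year), and the secondary analyses are descriptive.

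**Recurrent bleeding.** Section 9.7.3.1 says: "In subjects who experience recurrent bleeding episodes, the Investigator and Medical Monitor will discuss whether to resume prior FVIII prophylaxis or use of emicizumab". It sets no limit by prior therapy. Section 9.1, like the synopsis, says only: "In subjects who experience recurring bleeding episodes, the Investigator and Medical Monitor will discuss whether to resume prior FVIII prophylaxis". Emicizumab is not on the list of prohibited medications in Section 9.4.8.

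**Missing data.** Section 14.3 of the original protocol says: "The missing value of the change for annualized utilization and annualized infusion rate will be imputed as 0". The text available for this review ends before Section 14.3 of Amendment 1. The amendment's summary of changes lists no analysis change, but whether the rule still stands could not be confirmed.

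**The concern.** A subject whose bleeding recurs after BMN 270 and who goes back to prophylaxis is a treatment failure in any ordinary sense. Section 9.1 itself defines failure partly by loss of independence from prophylactic FVIII. As the endpoint is written, the score of such a subject depends on which prophylactic is used. A return to FVIII is counted in full. A move to emicizumab is hardly counted, because FVIII then accrues only for treated bleeds.

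What is at stake is the mean reduction in FVIII use and its confidence interval. Both could look better because one prophylactic had replaced another, and a reader of the table could not tell this from freedom from prophylaxis. Under the original protocol's missing-data rule, a subject with unknown use is scored as no change, which is stricter than the score of a documented failure on emicizumab.

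**Working it through.** The protocol states no figure for this endpoint. The one calculated figure in the plan, 85% power for the primary test (n = 16, effect size 0.8, one-sided 0.025), reproduces as 84.8% from the noncentral t with 15 df and noncentrality 0.8 × √16 = 3.2. The present point does not touch it.

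**Inputs**
- Prophylaxis frequency r = 2 to 3 infusions per week (synopsis, Study Rationale). Baseline is 52r, or 104 to 156 infusions/year.
- Window: Weeks 5-52, which is 48 weeks.
- Assumed, because the documents give no values: number of FVIII-treated bleeds, two infusions per bleed, week of change, and the same dose for bleeds as for prophylaxis. With an equal dose per infusion, IU/kg and infusion counts give the same percentages.

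**Formula.** With I FVIII infusions in the window, the annualized rate is I × 52/48, so the change as a share of baseline is I/(48r) - 1. The denominator 48r is 96 at two per week and 144 at three. Percentages are used here only to put subjects on one scale.

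| Course of a failure in Weeks 5-52 | 2 per week | 3 per week |
|---|---|---|
| Emicizumab, 2 treated bleeds (I = 4) | -95.8% | -97.2% |
| Emicizumab, 4 treated bleeds (I = 8) | -91.7% | -94.4% |
| Emicizumab, 8 treated bleeds (I = 16) | -83.3% | -88.9% |
| Emicizumab, no treated bleed (I = 0) | -100% | -100% |
| FVIII restarted Week 20, no on-demand use (I = 33r) | -31% | -31% |
| FVIII restarted Week 13, 8 earlier on-demand infusions (I = 40r + 8) | -8.3% | -11.1% |
| FVIII restarted Week 26, same (I = 27r + 8) | -35.4% | -38.2% |
| FVIII restarted Week 39, same (I = 14r + 8) | -62.5% | -65.3% |

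**Effect on the mean.** FVIII given before the change is the same on either course. With no on-demand FVIII afterwards, the gap between the two courses for a change at Week w is (53 - w)/48 of baseline, and one subject moves the mean of n by that gap divided by n. The number of prior-FVIII subjects is not given, so n = 16 is an assumption.
- Week 20: 33/48 × 104 = 71.5 and 33/48 × 156 = 107.25 infusions/year. Divided by 16 this is 4.5 to 6.7 infusions/year, or 4.3% of baseline.
- Week 8: 45/48/16 = 5.9%.
- Week 40: 13/48/16 = 1.7%.

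**Several subjects.** At three infusions per week and 8 on-demand infusions each, with the other subjects at -100%, 1, 2 or 3 failures on emicizumab give means of -99.7%, -99.3% and -99.0%. If the same subjects restart FVIII at Week 26, the means are -96.1%, -92.3% and -88.4%.

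**The case against.** **A reader might infer that such a failure scores zero FVIII use, exactly like a full responder.** The documents do not support that as a general statement. The trigger is recurrent bleeding, acute bleeds may be treated with FVIII (Section 9.4.8.1), and the synopsis says patients on emicizumab still need FVIII for breakthrough bleeds. All of that use counts. A score of -100% needs a window without one FVIII-treated bleed.

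**A reader might infer that the protocol clearly permits the switch in prior-FVIII subjects.** It does not. The emicizumab clause in Section 9.7.3.1 can be read as each subject resuming what he had before, and the synopsis and Section 9.1 name only FVIII. Its absence from the prohibited list is weak evidence, since that list applies from before Screening and one planned stratum stays on emicizumab until infusion. The restriction is nonetheless unwritten, and the passages differ.

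**The endpoint measures what its label says.** Section 8 states the aim as the impact on use of exogenous FVIII, not freedom from all prophylaxis. It is therefore too strong to say that the derivation reverses its purpose. This also argues against overwriting observed FVIII use in the main analysis; a value meant for missing data is no warrant for that.

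**Handling of rescue therapy often sits in the SAP, and other endpoints would show the failure.** The first part stands for detail, but here the protocol itself fixes an FVIII-only count. The second is partly true: FVIII activity and treated bleeds would give some sign. However, the synopsis says bleed rates on emicizumab are lower than on prior FVIII prophylaxis, so bleeding after a switch may look improved, and neither measure corrects the utilization mean.

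**Conclusion.** The point holds as a gap in a descriptive secondary endpoint. If a prior-FVIII subject is moved to emicizumab, the endpoint scores that failure at about -83% to -97% of baseline, against about -31% for the same failure restarted on FVIII at Week 20 without on-demand use. At an assumed n = 16, each such subject favours BMN 270 by up to about 4% of baseline for a Week 20 change, with 5.9% at Week 8 and 1.7% at Week 40. In a smaller stratum each subject would weigh more.

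These sizes rest on assumed bleed counts, infusions per bleed and timing. They also assume that the switch happens at all, and the protocol gives no expected number. The primary test, its power and its error rate are unaffected. It would be wrong to conclude that the reported reduction in FVIII use is already biased: the documents support only that it would be if such switches occur.

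**What to change.** Keep observed FVIII use as the endpoint. In the synopsis and Section 14.3, pre-specify:

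1. **Reporting beside the endpoint:** the number of prior-FVIII subjects who start emicizumab or any other non-FVIII prophylaxis in Weeks 5-52, their time on it, and the number on any prophylaxis at Week 52.
2. **A supplementary analysis:** time from the first such dose to Week 52 is scored at the subject's own baseline FVIII rate, that is, no change for that time. A Week 20 switcher with 8 earlier on-demand infusions would then score (8 + 33r)/(48r) - 1, or -22.9% at two per week (74/96) and -25.7% at three (107/144). This equals the score of the same failure restarted on FVIII at Week 20 with no later on-demand use.

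The synopsis and Section 9.1 must also be reconciled with Section 9.7.3.1 on what may be considered after recurrent bleeding. Which option applies is for the sponsor to settle.

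The cost is wording. Section 9.4.8 already requires concomitant medications added or discontinued during the study to be recorded on the eCRF. The downside is that the reduction shown in the supplementary analysis may be slightly less favourable.
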